16.4 Expanded Disability Status Scale (EDSS)

Descriptive statistics for the EDSS score and EDSS CFB at each visit during the DBP and the OLE period combined will be provided by treatment group and overall on the mITT analysis set.

In addition, descriptive statistics for the EDSS score and EDSS CFB at each visit during the OLE period only will be provided by treatment group and overall on the mITT-OLE analysis set (early treatment discontinuers during OLE will be presented at 'EOT' visit).

Descriptive statistics for categorical EDSS CFB, i.e., number and proportion improving, stable, or worsening, will also be reported for each time point. Here improvement is defined as a decrease of 1.0 point or more, stable condition as a change of no more than half a point in either direction and worsening as an increase of 1.0 point or more.

Mean CFB in EDSS will be presented on mITT analysis set as a by-year line plot during DBP and OLE period combined. The plot will be provided for each treatment group and overall, with a vertical line segment at each visit representing \pm SE (jittered if needed for legibility), and with all treatment groups included in a single figure.

Additionally, the plot of mean CFB in EDSS will be presented for OLE period only (OLE Week 48 to OLE Week 336 and EOT) on mITT-OLE analysis set.

A listing will be provided for EDSS data, by participant and by timepoint for the DBP and OLE treatment period combined.

17 Safety Evaluation

The subsections in this section include specifications for summarizing safety endpoints that are common across clinical trials such as adverse events, laboratory tests and vital signs.

All outputs will be provided on the OLE period if not otherwise indicated.

Safety analyses will be based on the SAF for summaries on the DBP + OLE period and on the SAF-OLE for summaries on the OLE period, according to the as-treated principle.

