5.6.1 Withdrawal from Trial Therapy

Participants who withdraw from therapy (during the 48-week main study or OLE Period) must immediately return for an End of Treatment Visit or an OLE End of Treatment Visit followed by the 4-week Safety Follow-Up/End of Trial Visit 4 weeks later (see Section 7.1.5 and 7.1.6). A participant must be withdrawn if any of the following occur:

- Withdrawn from study (see Section 5.6.2);
- AEs, if discontinuation of IMP is desired or considered necessary by the Investigator and/or participant;
- Use of prohibited medications, as defined in Section 6.4.2. However, any medications that are considered necessary for the participant's well-being may be given at the discretion of the Investigator. Use of a prohibited medication may be cause for a participant to withdraw, however each incident should be discussed on a case-by-case basis with the study and Medical Monitor;
- Pregnancy;
- Lack of efficacy and/or progression of MS as defined by Investigator judgment or when a medication other than protocol-allowed medications is needed for treatment;
- Any events that unacceptably endanger the safety of the participant;
- IMP will be discontinued in case of elevated liver tests as defined in protocol Section 6.4.4.
- If any of the following occur while a participant is receiving Tecfidera (17, 18):
 - Any instance of lymphocyte counts < 200/mm³ or < 500/mm³ for > 24 weeks
 - In the event of serious infection, Tecfidera should be withheld until the infection is resolved
 - At the first sign or symptom suggestive of PML
 - More than 1 instance of dose reduction due to a flushing reaction (see Section 6.4.4 or the local label [17, 18]) and GI disturbances.

Withdrawal due to special precautions is described in Section 6.4.4.

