The purpose of this Integrated Analysis Plan (IAP) is to document technical and detailed specifications for the Final Analysis (FA) of data collected for protocol MS200527-0086 considering the early termination of the study; the primary endpoints of the phase 3 MS200527_0080 and MS200527_0082 studies were not met). The IAP is based upon Section 8 (Statistics) of the trial protocol dated 06 July 2023 (Version 8.0) and is prepared in compliance with International Conference on Harmonization E9.

This FA data report will include summaries of participant disposition, demographics, baseline characteristics, medical history, previous and concomitant medications, treatment exposure, efficacy evaluations, adverse events (AEs), deaths, selected laboratory parameters, vital signs, ECGs, and other endpoints related to safety monitoring up to the end of the study.

6 Objectives/Endpoints of the Final Analysis

The objective of the OLE Period of this study is to evaluate the long-term safety, efficacy, and HRQoL of M2951 for an additional 8 years, at an initial dose of 75 mg once daily which was eventually switched to 75 mg twice daily.

Endpoints for OLE Period:

- Efficacy and CCI endpoints at Week 48, 96, 144, 192, 240, 288, 336 and 384.
 - Number of gadolinium-enhancing T1 lesions;
 - ARR, based on protocol-defined qualified relapses;
 - Qualified relapse-free status;
 - Change from baseline in disability score based on EDSS score;

Safety as assessed by the nature, severity, and occurrence of AEs; vital signs; ECGs; absolute concentrations and change from Baseline in Ig levels;
 ; and clinical laboratory safety parameters.

For the Final Analysis, selected safety and efficacy endpoints based on data from OLE Day 1 to the end of the study will be evaluated.

For more details on the main study objectives please review section 4 Trial Objectives of the protocol.

7 Sample Size/Randomization

Sample size and randomization is described in the IAP for the primary analysis/blinded extension analysis performed after completion of the Double-Blind Period (DBP) of the study (Week 48/Week 52).

8 Overview of Planned Analyses

The protocol describes a total of 5 analyses that should be performed for this study. 4 of them have already been conducted according to the protocol. These are:

- Primary Analysis (when 100% of participants enrolled reached Week 24 of treatment, or prematurely discontinued from treatment)

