11.5 Presentation of continuous and qualitative variables

Continuous variables will be summarized using descriptive statistics, i.e.:

- number of participants (N)
- number and percentage of non-missing values
- number and percentage of missing values.
- mean, standard deviation (SD)
- median, 25th Percentile 75th Percentile (Q1-Q3)
- minimum, and maximum

The number of digits for non-derived and derived data, presented in outputs or available in ADaM (Analysis Data Model) datasets, is specified in the Biostatistics Outputs Assembly (BOA) document.

For both continuous and qualitative variables, percentages as 0% or 100% should be reported with the same format used for the column and together with the count of values. For example, if the count of value is zero, then display '0 (0.0)'; if the percentage is 100% then display 'xx (100.0)'.

Qualitative variables will be summarized by counts and percentages. A missing category should always be displayed at baseline – even when no missing data. A missing category, at other endpoints than baseline, should only be displayed when there are missing data.

Unless otherwise stated, the calculation of proportions will be based on the number of participants in the analysis set of interest. Therefore, counts of missing observations will be included in the denominator and presented as a separate category.

In case the analysis refers only to certain visits, percentages will be based on the number of participants in the analysis set of interest, unless otherwise specified. Total of missing and non-missing observations at each time-point will reflect the population still in the trial at that time. For example, if a participant is still in the trial at the time-point but with missing data, it should be counted in the number of missing observations.

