11.9 Handling of missing data

Unless otherwise specified, missing data will not be replaced.

In all participant data listings, imputed values will be presented and flagged. Partial dates, which are not to be imputed according to this IAP, will be presented using the format "____YYYY".

Missing statistics, eg, when they cannot be calculated, should be presented as 'nd', with 'nd' standing for 'not done'. For example, if n = 1, the measure of variability (SD) cannot be computed and should be presented as 'nd'.

In case of zero records available for presentation in a given TLF, then an empty output with 0 occurrence or a sentence stating that there are no data will be provided. For tables of Adverse Events and Deaths (outputs required for EudraCT and/or clinicaltrial.gov), if there is no observation, the output must contain the first line 'Participant with...' or 'Participant who died' displayed with 0 occurrence.

If a System Organ Class (SOC) or Anatomical Therapeutic Class (ATC) term is missing/not coded yet, then 'Uncoded SOC' (or 'Uncoded ATC') will be indicated at the TLF level. When a Preferred Term (PT) is missing, it will be set to 'Uncoded PT:' TEAE verbatim text.

Incomplete AE-related dates will be handled as follows:

- In case the onset date is missing completely or missing partially but the onset month and year, or the onset year, are equal to the start of IMP, then the onset date will be replaced by the minimum of the start of IMP date and the AE resolution date (if not missing).
- In all other cases the missing onset day or missing onset month will be replaced by 1.
- Incomplete stop dates will be replaced by the last day of the month (if day is missing only), if not resulting in a date later than the date of participant death. In the latter case, the date of death will be used to impute the incomplete stop date.

Participants with study termination e-CRF form completed and treatment termination form missing at the time of the end of study will be handled as follows:

End of treatment status will be set to "Discontinued" and the following end of treatment information will be carried over from the study termination e-CRF form:

- Reason for discontinuation of treatment will be replaced by the reason for study discontinuation
- Reason for discontinuation of treatment protocol non-compliance/withdrawal of consent/Other, specify free-text fields will be replaced by the corresponding free-text fields in the study termination form

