11.12 Early treatment termination assessments

By-visit summary statistics should be programmed based on assessments slotted according to the visit windowing approach described below. A by-visit summary table/figure will include a footnote indicating whether assessments from early treatment termination visits are included in the analysis based on slotting the assessment into the appropriate analysis visit window. The summary for the Early Treatment Termination visit (for assessments not slotted according to a visit window approach) will be distinguished from the OLE Week 384 visit, and the Early Study Termination visit from the summary for the OLE Week 388 visit.

For analyses by time period, data from Safety Follow-up will be included in the period in which the participant has discontinued. Data from Safety Follow-up will also be included in shift table to derive worst grade or value.

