11.13 Analysis visit windows

Assessments may be made at times other than the nominal times of planned visits, due to participant scheduling issues, unscheduled visits, or early treatment termination visits.

Analysis visit windows for efficacy and safety endpoints, will be used to incorporate unscheduled assessments in by-visit summaries. For participants discontinuing treatment during the OLE, the premature End of Treatment (EOT) assessment will be windowed appropriately, prior to the analysis, for safety.

For the calculation of analysis visit using the time windows, 1 month is expressed as 30 days.

As the schedule of assessments is different for each visit, specific time windows must be used for each endpoint. They are defined in Appendix 19.3.

For all biochemistry parameters, the same schedule of assessment is considered with all visits possible per protocol.

If there are multiple assessments within a same visit window, then the one closest to the target day will be used. If 2 assessments have the same difference with target day, the earlier one will be used.

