16.1 MRI

Descriptive statistics for the number of T1 Gd+ lesions, new/enlarging T2 lesions and T2 volume at each visit (early treatment discontinuers during OLE will be presented at 'EOT' visit) during the OLE will be provided by treatment group and overall on the mITT-OLE analysis set.

Mean number of T1 Gd+ lesions and new/enlarging T2 lesions will be presented as a by-visit line plot for each treatment group during the OLE on the mITT-OLE analysis set, with a vertical line segment at each visit representing ± standard error (SE) (jittered if needed for legibility), and with all treatment groups included in a single figure.

A listing will be provided for the MRI assessment data, by participant and by timepoint for the OLE treatment period.

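### Late OLE visit rows for EDSS and MRI describe participants still on treatment, because early leavers' final values go to one pooled 'EOT' row; EDSS worsening is likely to be understated there, by an amount the documents do not allow us to fix

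*SAP*

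**What the plan says.** SAP 6 lists as an OLE endpoint "Change from baseline in disability score based on EDSS score", at OLE Weeks 48 to 384, alongside the number of Gd+ T1 lesions.

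SAP 16.4 plans by-visit EDSS statistics for the OLE alone on mITT-OLE, with the rule that "early treatment discontinuers during OLE will be presented at 'EOT' visit". The OLE-only plot of mean change runs over Weeks 48 to 336 and also shows EOT. SAP 16.1 applies the same rule to "Descriptive statistics for the number of T1 Gd+ lesions, new/enlarging T2 lesions and T2 volume at each visit".

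The general sections handle early-termination data differently:
- SAP 11.12: "By-visit summary statistics should be programmed based on assessments slotted according to the visit windowing approach described below". A footnote must say whether early-termination assessments are included.
- SAP 11.13: for OLE discontinuers, "the premature End of Treatment (EOT) assessment will be windowed appropriately, prior to the analysis, for safety".
- SAP 11.9: "Unless otherwise specified, missing data will not be replaced".
- SAP 11.5: "Total of missing and non-missing observations at each time-point will reflect the population still in the trial at that time".

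Protocol 5.6.1 lists among the events after which a participant must be withdrawn from therapy: "Lack of efficacy and/or progression of MS as defined by Investigator judgment". Protocol 7.1.6 requires early discontinuers to attend the OLE End of Treatment Visit. Protocol Table 3 includes EDSS and MRI at that visit.

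**The concern.** Each yearly row in these tables contains the people who have not yet left. If some left because their MS progressed, the rows lose the worst courses as time passes, and the mean EDSS change and the improved/stable/worsened percentages look better than they would for everyone who began the OLE. The leavers' last values sit in a single row that mixes departures from the first weeks with departures years later, so the row cannot be read against time.

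The link between outcome and departure is built into the trial's conduct. Besides the withdrawal rule, Protocol 2 and 7 have a CRO neurologist review EDSS systematically for lack of efficacy or progression. Protocol 6.4.2 treats the start of a new immunosuppressant or immunomodulator as treatment failure leading to withdrawal.

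Long-term efficacy is an OLE objective, and a flat EDSS curve over several years is easily read as a sustained effect. The relapse analyses are protected better. The annualized relapse rate in SAP 16.2 uses discontinuers' events and follow-up time, and SAP 16.3 counts qualified relapses after treatment stops.

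**Working it through.** **Text check.** SAP 16.1 and the OLE-only part of 16.4 give a specific instruction (EOT row) that displaces the general slotting rule in 11.12. SAP 11.13 does not restore slotting for efficacy, because its statement on premature EOT values is confined to safety. With no replacement of missing data and no model in SAP 16, nothing places those EDSS or MRI values at the time they were obtained.

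The combined DBP+OLE EDSS table and plot on mITT carry no EOT rule. There 11.12 points to slotting while 11.13 mentions safety only, so the handling is unclear.

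**Illustration of size.** The plan states no figure to reproduce, and the inputs are partly assumed:
- Drop-out of 12% per year. This is the main-study planning value (Protocol 5.1 and 8.1: 44/(1 − 0.12) = 50 per group). Carrying it into the OLE is an assumption.
- OLE entrants: 250 × 0.80 = 200 (Protocol 8.1).
- q, the share of leavers who left for progression: 0 to 40%, assumed.
- mp − ms, the excess EDSS change in those leavers over stayers: 1.0 to 2.0 points, assumed.
- Other leavers are assumed to have the same mean as stayers.

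Share departed by OLE week w: d = 1 − 0.88^(7w/365.25).

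| OLE week | Years | Still on treatment | Of 200 | d |
|---|---|---|---|---|
| 96 | 1.84 | 0.790 | 158 | 0.210 |
| 240 | 4.60 | 0.555 | 111 | 0.445 |
| 336 | 6.44 | 0.439 | 88 | 0.561 |

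The mean over everyone is (1 − d)·ms + d·[q·mp + (1 − q)·ms] = ms + d·q·(mp − ms). The stayers' row shows ms, so the gap is d·q·(mp − ms). At Week 240 with q = 0.40 and 2.0 points: 0.445 × 0.40 × 2.0 = 0.356.

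| OLE week | q = 0 | q = 10% | q = 20% | q = 40% |
|---|---|---|---|---|
| 96 | 0 | 0.02–0.04 | 0.04–0.08 | 0.08–0.17 |
| 240 | 0 | 0.04–0.09 | 0.09–0.18 | 0.18–0.36 |
| 336 | 0 | 0.06–0.11 | 0.11–0.22 | 0.22–0.45 |

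**What windowing alone recovers.** In Appendix 19.3 the EDSS window for OLE Week 48 is days 169 to 503, target 336. A participant seen on day 336 who leaves on day 400 has both values in that window. The closest-to-target rule keeps day 336 and drops the EOT value. If the same participant leaves on day 600, the EOT value fills the Week 96 row (days 504 to 839). Later rows stay empty in both cases, so windowing helps but corrects only part of the selection.

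**The case against.** The strongest reply is that nothing is hidden. Leavers' earlier visits count in earlier rows, and their last values appear in the EOT row and the listings and, for EDSS, in the OLE-only plot. SAP 12.1 tabulates discontinuations by OLE interval and reports reasons, and SAP 11.5 makes the shrinking denominator visible. The analysis is purely descriptive. Unscheduled EDSS assessments for neurological worsening (Protocol 7.1.4) are windowed into by-visit summaries under SAP 11.11 and 11.13, so some worsening before departure can reach the yearly rows. Withdrawal rests on Investigator judgment with no EDSS threshold, and Protocol 6.4.1 says a relapse alone is not a reason.

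All of this stands, and it limits the point. It does not remove it: visible attrition does not correct a late row, and a pooled EOT row cannot be matched to a year.

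A reader might infer more than the documents support:
- **That EDSS change is understated as a fact, or by a stated percentage.** The share leaving for progression is not given, the gap can be zero, and any percentage needs a true EDSS slope that the documents do not supply.
- **That every OLE EDSS output is affected.** The EOT rule is attached only to the OLE-only EDSS summaries. For the combined outputs, exclusion is not established.
- **That Gd+ counts are biased to a similar degree.** No size has been worked out for them. The local MRI report to the Treating Investigator covers only non-MS pathology (Protocol 7.3.1), so any selection on lesions would be indirect.

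**Conclusion.** The point holds for the OLE-only EDSS summaries and the OLE MRI summaries: late visit rows describe participants still on treatment. For EDSS they are likely to understate worsening, because progression is a required ground for withdrawal and the plan has no analysis that uses the final values in time. Illustratively, the gap is 0 to about 0.36 points at OLE Week 240, and 0.04 to 0.09 if 10% of leavers progressed. It is zero if nobody leaves for progression. These figures rest on the 12% allowance carried into the OLE, the assumed q and excess worsening, and other leavers resembling stayers. They also treat the excess as still present at the later visit, although leavers may take other treatment and are followed for only about four weeks.

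For MRI, the mixing of departure times in the EOT row is established; the direction and size of any bias in lesion counts are not. This is a worthwhile, inexpensive improvement to a descriptive analysis, not an error that invalidates it.

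**What to change.** 1. In SAP 16.4, add a supportive repeated-measures mixed model for EDSS change from OLE baseline, using every OLE EDSS value with the premature EOT value at its actual day. Report model-based means by OLE year, by initial group and overall. Keep the planned descriptive display as the main one.
2. In SAP 16.1 and 16.4, add by-visit summaries with premature EOT EDSS and MRI values slotted into the Appendix 19.3 windows. State the same handling for the combined DBP+OLE EDSS table and plot, with the footnote that 11.12 requires.
3. Keep the EOT row, split by time and reason for discontinuation. Show it off the time axis in the plot, and label the observed-case rows as participants still on treatment.

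Cost: SAP wording, one model and some additional tables; the End of Treatment EDSS and MRI are already scheduled. Downsides: the model assumes that departure is explained by observed EDSS and treats an ordinal scale as continuous, and windowing alone corrects only part of the bias. That is why both are proposed as supportive.

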17.1 Adverse Events

Treatment-emergent adverse events (TEAEs) are defined as those AEs with an onset date on or after the date of first IMP administration or with an onset date prior to first IMP administration, but an exacerbation date after. For the DBP the reference date is first study IMP administration date. For the OLE period, the reference date is first administration of Evobrutinib during the OLE period.

TEAEs occurring during the 4 weeks of Safety Follow-up will be included in the tables.

TEAEs occurring during the wash-out period for participant treated with Tecfidera during the DBP will be flagged in the listing of TEAEs from the overall study.

In case a subject entered the gap period allowed at OLE Week 96, the AE starting during this period will be considered as starting also during the OLE period and then considered as TEAE in the analyses. These AEs will be flagged in the listing of all TEAEs.

Trial drug related Adverse Events are those AEs with relationship to study treatment reported by the investigator as related or those of unknown relationship.

Serious Adverse Events are those events reported on the AE eCRF form with the serious field ticked "Yes" or with unknown seriousness.

Adverse Events leading to study withdrawal of IMP are those AEs with action taken regarding study treatment as "Drug withdrawn" (as recorded on the AEs eCRF page).

Adverse Events leading to study termination are those AEs with other action taken as "Led to study termination" (as recorded on the AEs eCRF page).

Adverse Events leading to death are those AEs with outcome "Fatal" (as recorded on the AEs eCRF page).

Adverse events will be coded according to the latest MedDRA version available at the time of analysis. The severity of AEs will be graded using National Cancer Institute - Common Terminology Criteria for AEs (NCI-CTCAE version 4.03) toxicity grades.

All Adverse Events recorded during the course of the trial (i.e., assessed from signature of informed consent until the end of the Follow-up/End of Trial visit) will be coded according to the MedDRA and assigned to a SOC and PT.

Group/SOC terms will be sorted alphabetically. Preferred terms within each group/SOC will be sorted by the Total column descending frequency, and alphabetically if multiple preferred terms have the same frequency.

If a participant experiences more than one occurrence of the same TEAE during the trial for a given trial period of interest, the participant will only be counted once for that treatment (the worst severity and the worst relationship to trial treatment will be tabulated).

In case a participant had events with missing and non-missing grades, the maximum of the non-missing grades will be displayed. AEs with missing classification concerning study intervention relationship will be considered related to the study intervention.

Incomplete AE-related dates will be handled as described in Section 11.9.

